APPENDIX 3 - DEFINITIONS

Adverse Device Effect (ADE): An adverse device effect is defined as any untoward adverse event related to the use of an investigational or unintended response to a medical device.

NOTE 1: This definition includes adverse events resulting from insufficient or inadequate Instructions for Use, deployment, installation, operation, or any malfunction of the medical device. This definition includes any event resulting from insufficiencies or inadequacies in the Instructions for Use or the deployment of the device or any event that is a result of user error.

NOTE 2: This definition includes any event resulting from use error or from intentional misuse of the medical device.

Adverse Event (AE): An adverse event (AE) is any untoward medical occurrence, unintended disease or injury, or untoward clinical signs (including abnormal laboratory findings) in subjects, users or other persons, whether or not related to the study device/procedure.

Anemia: Decrease from baseline in red blood cells, hemoglobin, or total blood volume that is associated with hemodynamic changes or requires transfusion, or a drop in hematocrit to below 30%. Any documented anemic event requiring ≥ 2 units PRBCs will be considered an SAE.

Bleeding Complication at Index Procedure: Bleeding requiring intra-procedure intervention is not considered a serious adverse event and while it can occur it can be managed intra procedurally.

Death: (divided into 2 categories)

A. Cardiac death is death due to any of the following:

1. Acute myocardial infarction.
2. Cardiac perforation/pericardial tamponade.
3. Arrhythmia or conduction abnormality.
4. Stroke within 30 days of the procedure or stroke suspected of being related to the procedure.
5. Death due to complication of the procedure, including bleeding, vascular repair, transfusion reaction, or bypass surgery.
6. Any death for which a cardiac cause cannot be excluded.

B. Non-cardiac death is a death not due to cardiac causes (as defined immediately above).

Delayed Bleeding: Bleeding occurring after the patient has been discharged requiring hospitalization and intervention.

Bleeding that occurs post-procedure requiring intervention.

Device Failure: A device that is used in accordance with the Instructions for Use, but does not perform according to the Instructions for Use and negatively impacts the treatment.

Device Malfunction: A malfunction of a device is an unexpected change to the device that is contradictory to the Instructions for Use and may or may not affect device performance. Includes damage, stress fracture or other failure as observed at the procedure.

Endoscopy: An examination or procedure using an endoscope to examine the inside of the alimentary tract.

Infection, systemic: Systemic infection documented by positive lab culture or clinical evidence, requiring medical treatment to treat and resolve.

Perforation: Puncture of the alimentary tract.

Serious Adverse Device Effect (SADE): A serious adverse device effect is defined as an adverse device effect that results in any of the consequences characteristics of a serious adverse event or that might have led to any of these consequences if suitable action had not been taken or intervention had not been made or if circumstances had been less opportune.

Serious Adverse Event (SAE): A serious adverse event (SAE) is defined an adverse event that:

- led to death,
- led to a serious deterioration in the health of the subject, that either resulted in:
- a life-threatening illness or injury, or
- resulted in a permanent impairment of a body structure or a body function, or
- required in-patient hospitalization or prolongation of existing hospitalization, or
- resulted in medical or surgical intervention to prevent life-threatening illness or injury or permanent impairment to body structure or a body function, or,
- led to fetal distress, fetal death or a congenital abnormality or birth defect.

NOTE: Planned hospitalization for a pre-existing condition, or a procedure required by the study plan without serious deterioration in health, is not considered a serious adverse event.

Sepsis: Organ dysfunction, hypoperfusion, or hypotension in the presence of a known or suspected infection.

Unanticipated Adverse Device Effect (UADE): A UADE is an event that occurs that has not been expected to occur with the device or during the course of the study procedures and has not otherwise been identified as a possible risk in the clinical investigations.

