6.0 Risks / Benefits Assessment

6.1 Risks to the Patient

The EndoRotor procedure poses no new risks to the patient than the commonly used mucosal resection techniques. As with all endoscopic resection and ablation devices, the most common risks are perforation and bleeding requiring intervention. Bleeding requiring intra-procedure intervention is not considered a serious adverse event and while it can occur it can be managed intra procedurally. Subjects may experience discomfort and pain post-procedure and after one to two days of the procedure. Other commonly known risks to a resection or ablation device include the following:

- Delayed bleeding occurring after the patient has been discharged requiring hospitalization and intervention
- Undiagnosed perforation resulting in free air in the mediastinum post-procedure

These are all common to established mucosal resection / ablation techniques and endoscopists are well practiced in handling these events. There are no additional risks that are particular to the EndoRotor® mechanical resection devices.

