7.7 Safety Hypotheses

Safety is assessed by the rate of anticipated complications due to treatment. The primary complications expected are strictures, bleeding, and esophageal perforation). It is hypothesized that the complication rate in the EndoRotor arm will be no greater than in the control arm.

$$\begin{aligned} \text{Null Hypothesis: } & \text{Erate} > \text{Crate} \\ \text{Alternate Hypothesis: } & \text{Erate} < \text{Crate} \end{aligned}$$

Where:

Erate = Rate of Bleeding, Perforation and Stricture for EndoRotor

Crate = Rate of Bleeding, Perforation and Stricture for Control

Testing will be completed using Fisher's Exact test with two-tailed $\alpha = 0.05$

Further, subsets of complications assessed to be serious (e.g., serious adverse events) will be compared, as appropriate.

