10.2 Safety Monitoring & Study Termination

The Medical Monitor will closely monitor current medical practice, device performance, and the occurrence of and rate of occurrence of adverse events, serious adverse events, and unanticipated adverse device effects to determine if there is an unreasonable risk to the study participants. If warranted, the study protocol may be amended, and/or the study may be suspended or terminated early.

An independent Data Monitoring Committee (DMC) consisting of at least three members will review serious adverse events and safety endpoint events. Adjudication of adverse events will be conducted according to a Data Monitoring Committee Charter to be approved by the Sponsor and the DMC. The Charter will include:

- Stopping rules
- Planned Safety Reviews: Safety reviews will occur at predetermined intervals
- Unplanned Safety Reviews: Any safety concerns that arise during the trial will be brought to the attention of the IPA. A full DMC meeting can be called at the discretion of the DMC Chairperson. The DMC Chairperson may also request additional data reviews when considered necessary to monitor the progress of the trial.
- DMC reports are to include:
 - Rates of recruitment, ineligibility, noncompliance, protocol violations and dropouts, overall and by study site;
 - Completeness and timeliness of data;
 - Duration of follow-up and early study discontinuation;
 - Baseline characteristics and demographics;
 - Medical History;
 - Device data;
 - Adverse Events;
 - Serious Adverse Events; and
 - Unanticipated Adverse Device Effects
 - A significant difference in safety or effectiveness between the EndoRotor and the control devices
 - Decision on continuing or stopping the study based on safety and effectiveness of the study device and the control devices

The DMC will be determined prior to the study and records of event review will be documented and maintained in the study records. The DMC will be completely independent of the Sponsor and the ENDOROTOR study. The Sponsor may terminate Investigator and site participation in the study if there is evidence of an Investigator's failure to maintain adequate clinical standards or evidence of continued serious protocol deviations.

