10.4 Adverse Events & Definitions

A complication is defined as any clinical finding that has the potential to become clinically significant in the opinion of the investigator. A complication may progress in the level of clinical significance and become classified as an adverse event. All complications shall be recorded on the CRFs.

Adverse Events (AEs) are clinical findings that result in an untoward medical event.

Please record all AEs on the CRFs. Adverse Events will be further classified as Serious Adverse Events (SAEs) if the event:

- Is life threatening or fatal;
- Results in permanent impairment of a body structure or function;
- Results in congenital anomalies/birth defects
- Requires or prolongs hospitalization; or
- Requires medical or surgical intervention to preclude permanent impairment of a body function or permanent damage to a body structure.

Note: Hospitalization is defined as any initial admission (even if less than 24 hours) to a healthcare facility as a result of a precipitating clinical adverse effect; to include transfer within the hospital to an intensive care unit. Hospitalization or prolongation of hospitalization in the absence of a precipitating, clinical adverse effect (e.g., for a preexisting condition not associated with a new adverse effect or with a worsening of the preexisting condition; admission for a protocol-specified procedure) is not, in itself, a serious adverse effect. The following definitions for rating severity of adverse events will be used:

Mild: Awareness of signs or symptoms, but easily tolerated; are of minor irritant type; causing no loss of time from normal activities; symptoms would not require medication or a medical evaluation; signs or symptoms are transient.

Moderate: Interferes with the subject's usual activity and/or requires symptomatic treatment.

Severe: Symptom(s) causing severe discomfort and significant impact of the subject's usual

activity and requires treatment.

AEs or SAEs will also be classified as to their relationship to the device, as follows:

Not Related: The event is due to an underlying or concurrent illness or effect of another device, drug or intervention and is not related to the investigational device, procedure or general surgery.

Possible: The event has a strong temporal relationship to the use of the investigational device, procedure or general surgery, and an alternative etiology is equally or less likely.

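### The blanket rule that intra-procedure bleeding is never an SAE contradicts the general SAE criteria, delayed bleeding has two definitions, and Section 7.7 does not say which bleeds count

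*Combined protocol and SAP*

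**What the plan says.** **Intra-procedure bleeding.** Appendix 3, under an entry for bleeding complications at the index procedure, says "Bleeding requiring intra-procedure intervention is not considered a serious adverse event and while it can occur it can be managed intra procedurally". Section 6.1 repeats the rule ("Bleeding requiring intra-procedure intervention is not considered a serious adverse event") without limiting it to the index procedure.

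**General seriousness criteria.** Section 10.4 classifies an adverse event as serious if, among other criteria, it is life-threatening or fatal, or "Requires or prolongs hospitalization; or" needs intervention to preclude permanent impairment or damage. Its note counts any initial admission caused by an adverse effect, even one shorter than 24 hours. The SAE entry in Appendix 3 has similar criteria. The anemia entry adds: "Any documented anemic event requiring ≥ 2 units PRBCs will be considered an SAE". None of these exempts bleeding during a procedure.

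**Delayed bleeding.** Appendix 3 gives two statements under one heading: "Bleeding occurring after the patient has been discharged requiring hospitalization and intervention", then "Bleeding that occurs post-procedure requiring intervention". Section 6.1 carries only the first.

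**Use in the analysis.** Section 7.7 tests a combined complication rate by Fisher's exact test, two-tailed at 0.05 ("Erate = Rate of Bleeding, Perforation and Stricture for EndoRotor", with a matching control rate). It adds a comparison of the serious subset, as appropriate. Under Section 10.2 the DMC "will review serious adverse events and safety endpoint events".

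**The concern.** Section 6.1 names perforation and bleeding requiring intervention as the most common risks, so bleeding is central to the safety assessment. Its seriousness label decides three things: whether the sponsor hears within 24 hours (Sections 8.3, 8.6.1, 8.7 and 10.5), whether the event can become a device-related SAE (Section 10.4), and whether it enters the serious-subset comparison (Section 7.7). If two parts of the protocol give opposite labels, sites can classify the same bleed differently while each follows the text.

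The second weakness concerns the tested rate itself. Section 7.7 does not restrict that rate to serious events, so the SAE label does not decide membership. What is missing is any statement of which bleeds belong in it. Two delayed-bleeding thresholds, plus an intra-procedure entry that speaks only to seriousness, leave the count open to site interpretation.

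**Working it through.** The plan states no bleeding rate, SAE rate or power for the safety comparison that could be reproduced. The check is therefore a comparison of the texts, followed by a short calculation of how sensitive the test is to a single event.

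**Step 1. Seriousness of a bleed treated during the procedure**

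| Course of the bleed | Bleeding statement (6.1, Appendix 3) | Section 10.4, Appendix 3 SAE and anemia entries |
|---|---|---|
| Controlled through the scope, no further consequence | Not an SAE | Generally not an SAE |
| Life-threatening, treated on the spot | Not an SAE | SAE |
| Treated, then admitted, even for under 24 hours | Not an SAE | SAE |
| Treated, with anemia needing 2 or more units | Not an SAE | SAE under the anemia entry |

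The first row shows no conflict; the other three do. Whether stopping a bleed endoscopically could by itself meet the intervention criterion is a matter of judgement, and I do not count it as a contradiction.

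**Step 2. Repeat procedures.** Subjects may be treated twice (Section 4.2). The Appendix 3 heading confines the exemption to the index procedure and Section 6.1 does not, so a bleed at the second treatment falls under the exemption in one place but not the other.

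**Step 3. Delayed bleeding.** Call the narrower statement A (after discharge, with hospitalization and intervention) and the broader one B (post-procedure, with intervention).

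| Bleed | A | B |
|---|---|---|
| Treated in recovery, before discharge | No | Yes |
| After discharge, treated without admission | No | Yes |
| After discharge, admitted and treated | Yes | Yes |

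Every A event is a B event, but not the reverse.

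**Step 4. What Section 7.7 could be counting.** The wording is compatible with delayed bleeds by A only, delayed bleeds by B, B plus intra-procedure bleeds needing intervention, or any recorded bleed. These sets are nested, so the count can only grow from the first to the last.

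**Step 5. Sensitivity of the test to one event.** Take 55 per arm, the evaluable number in Section 4.5. With k events in one arm and none in the other, the two-tailed Fisher p value is 2 × C(55, k) / C(110, k).

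- k = 5: 2 × 3,478,761 / 122,391,522 = 0.057
- k = 6: 2 × 28,989,675 / 2,141,851,635 = 0.027

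Six events against none is therefore the smallest significant split. With one event in the other arm, the smallest significant count is 8. These are event counts on the combined endpoint, not predicted rates.

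**The case against.** The exemption goes on to say that such bleeding can be managed during the procedure, which suggests it was written for bleeds controlled there and then. For those there is no conflict. That is a fair reading of intent, but the sentence as printed has no exception.

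The anemia entry stands on its own, so a subject needing 2 or more units would still generate an SAE. This is right as far as it goes. The event would, however, be captured as anemia, while the bleed itself stayed non-serious and could be missing from the serious subset of bleeding, perforation and stricture. Admission without transfusion is not covered at all.

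B contains A, and B stands as a separate paragraph, so a label may simply be missing. Even then, Section 7.7 would not say which definition it uses.

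A reader might infer that these bleeds escape the DMC. The documents do not support that. Section 10.2 gives the DMC safety endpoint events as well as SAEs and lists adverse events among its report contents. Section 6.2 has it monitor and adjudicate adverse events generally. Section 10.4 requires all complications and adverse events to be recorded. This part of the objection stands in full: what is lost is SAE status and expedited reporting, not DMC review.

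**Conclusion.** The contradiction is real and confined to a subset: bleeds treated during a procedure that are life-threatening, lead to admission or need 2 or more units. For these, a site obeying the exemption would omit events from 24-hour reporting, SAE counts and the serious-subset comparison. The duplicate delayed-bleeding definition and the undefined bleeding component in Section 7.7 are separate gaps that could let sites count different events in the tested rate.

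The size cannot be derived from the plan. The calculation shows only that, at 55 per arm with few events, one event can move the result across 0.05.

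Three stronger readings are tempting but not supported:

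- **That the exemption hides mainly EndoRotor events.** It is worded for either arm, and Section 6.1 treats these risks as common to resection and ablation. A larger effect in the EndoRotor arm is plausible, because Section 5.5.3 takes resection down to the muscularis propria while Section 1.1 describes ablation as a surface treatment. It remains an assumption.
- **That the figures in Section 2.2 size the effect.** The pig bleeding grades are per resection site, pooled over colon, stomach and esophagus. The 1-16% range is the published rate for current techniques, set against 0.8% of sites for EndoRotor. Neither is a per-subject EndoRotor rate.
- **That the Section 10.4 definition of a complication sweeps in every minor bleed.** It requires potential clinical significance in the investigator's opinion.

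**What to change.** 1. Reconcile Section 6.1, Section 10.4 and the Appendix 3 bleeding, anemia and SAE entries. Either word the bleeding statement so that it does not override the general SAE criteria, or state explicitly which rule takes precedence. Apply the same rule to index and repeat procedures.
2. Keep one definition of delayed bleeding and use it in both Section 6.1 and Appendix 3.
3. In Section 7.7, prespecify a single bleeding component for both arms and all procedures. The threshold is for the sponsor to choose. Tabulate intra-procedure and later bleeds separately.

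The cost is wording in Sections 6.1, 7.7 and Appendix 3 (and 10.4 if precedence is stated there), plus a CRF field for the timing of the bleed and any SAE criterion met. Reported SAE and bleeding counts may be slightly higher. Because expedited reporting is affected, the change belongs before the first subject is treated.
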